5.3.2 Non-investigational medicinal products

Non-investigational medicinal products (NIMP) comprise the following: OADs and insulin.

5.3.2.1 Oral antidiabetic medication

Any approved and marketed metformin, glitazone, SGLT-2 inhibitor or sulphonylurea product or combination products are allowed. Subjects treated with dipeptidyl peptidase-IV (DPP-IV) inhibitors are excluded from participating in the trial since DPP-IV inhibitors and GLP-1 receptor agonists should not be combined.

To mitigate sulphonylurea induced hypoglycaemia, subjects treated with sulphonylurea may be at randomisation be asked to reduce the sulphonylurea dose by 50% at investigator's discretion. The type and dose of other OADs must be kept constant throughout the trial, unless unacceptable hypoglycaemia occurs and cannot be managed by reduction of the basal insulin dose.

In case the type of OAD becomes unavailable during the course of the trial, it is allowed per the discretion of the investigator to shift to an alternative treatment within the same class.

5.3.2.2 Treatment with insulin throughout the trial

Any approved and marketed basal insulin (NPH insulin or insulin analogue) is allowed, at any dose, if used according to its prescribing information at screening. Once-daily or twice-daily dosing is allowed, according to dosing schedule at baseline.

To reduce the risk of hypoglycaemia associated with liraglutide 3.0 mg and lifestyle intervention, it is recommended that the dose of basal insulin is reduced by 15-20 % for subjects with HbA_{1c} ≤ 8 % (at investigator's discretion) at randomisation. Furthermore, the basal dose should not exceed the pre-trial insulin dose in the first five weeks of liraglutide escalation, unless deemed necessary by investigator to treat unacceptable hyperglycaemia.

During the trial, subjects will be required to perform self-measured plasma glucose (SMPG) on 3 consecutive days, each week prior to basal insulin adjustment and enter the values into the subject diabetes diary. In the weeks where no site visits are planned, subjects will adjust their insulin dose themselves, according to the algorithm described below ([Table 5-2](#), [Table 5-3](#), and [Table 5-4](#)). These algorithms are provided to the subject in the diary and is part of the diabetes diary training. In the weeks where phone- or face-to-face contact is conducted, investigator will review previous self-adjustments, and perform adjustment for the current week.

The insulin dose adjustments recorded in the diabetes diary, must be entered in the electronic case report form (eCRF).

Insulin dose adjustments

The aim of this trial is to demonstrate safety and effect of liraglutide 3.0 mg in subjects with T2DM treated with basal insulin. To this end, reaching similar levels of glycaemic control is important, regardless of background medication. Therefore, trial subjects are encouraged, as appropriate, to adjust insulin doses according to the below algorithm – with dose increase based on the mean of the three pre-breakfast SMPGs measured, and dose decrease based on at least one of the three pre-breakfast plasma glucose values equal to or below 3.9 mmol/L (70 mg/dL).

Subject using once daily basal insulin will measure SMPG before breakfast and adjust their dose based on the 3 SMPGs measured on three consecutive days prior to dose adjustment. It is recommended to adjust the basal insulin dose once weekly at the investigator’s discretion.

Subject using twice daily basal insulin will measure pre-breakfast and pre-dinner SMPG and adjust their evening dose based on the three pre-breakfast SMPGs, and their morning dose based on the three pre-dinner SMPGs measured on three consecutive days prior to dose adjustment.

Table 5–2 Increase of basal insulin dose

Mean of three pre-breakfast or pre-dinner SMPG		Increase of basal insulin dose
mmol/L	mg/dL	U
4.0 – 5.0	71 – 90	No adjustment
5.1 – 7.0	91 – 126	+ 2
7.1 – 8.0	127 – 144	+ 4
8.1 – 9.0	145 – 162	+ 6
> 9.0	> 162	+ 8

Table 5–3 Decrease of basal insulin dose

Lowest of three pre-breakfast or pre-dinner SMPG		Reduction of basal insulin dose
mmol/L	mg/dL	U
< 3.1	< 56	- 4 (or 10 % if the dose > 45 U)
3.1 – 3.9	56 – 70	- 2 (or 5 % if the dose >45 U)

Intensification with bolus insulin

Initiation of bolus insulin can be considered after the 5-week escalation period, and only after optimisation of basal insulin dose. These are the steps to take in situations where maximum fasting glycaemic control has been achieved and overall glycaemic control is still sub-optimal, and the investigator judges that bolus insulin is a necessary safety precaution.

Once bolus insulin is initiated, subjects will start measuring 4 SMPGs – pre-breakfast, pre-lunch, pre-dinner and at bedtime, on three consecutive days a week, prior to dose adjustment. It is recommended to adjust the bolus insulin dose once weekly at the investigator's discretion. Bolus dose adjustments may be performed according to the below algorithm ([Table 5-4](#)), using the frequency of pre-prandial and bedtime plasma glucose values as follows:

- Pre-breakfast bolus insulin should be adjusted according to the 3 consecutive pre-lunch SMPGs in the preceding 3 days
- Pre-lunch bolus insulin should be adjusted according to the 3 consecutive pre-dinner SMPGs in the preceding 3 days
- Pre-dinner bolus insulin should be adjusted according to the 3 consecutive bedtime SMPGs in the preceding 3 days

Table 5-4 Bolus insulin adjustment

SMPG values		Adjustment	Frequency rule
mmol/L	mg/dL	U	
≤ 3.9	≤ 70	- 1	≥1 SMPG below target
4.0-6.0	71-108	0	0-1 SMPGs above target No SMPG below target
> 6.0	> 108	+ 1	≥2 SMPGs above target No SMPG below target

Additional face-to-face visits may be scheduled if deemed necessary by site staff to achieve or maintain acceptable glycaemic control.

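### The basal insulin increase and decrease tables in Protocol 5.3.2.2 can both apply to the same three readings, and nothing says which prevails

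*Protocol*

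**What the plan says.** Protocol 5.3.2.2 has subjects measure glucose on three consecutive days each week and adjust basal insulin from those three values. Two tables apply.

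- Table 5-2 is indexed by "Mean of three pre-breakfast or pre-dinner SMPG". A mean of 4.0–5.0 mmol/L gives no change, 5.1–7.0 gives +2 U, 7.1–8.0 gives +4 U, 8.1–9.0 gives +6 U, and above 9.0 gives +8 U.
- Table 5-3 is indexed by "Lowest of three pre-breakfast or pre-dinner SMPG". A lowest value of 3.1–3.9 mmol/L gives −2 U (5% if the dose exceeds 45 U), and below 3.1 gives −4 U (10% if the dose exceeds 45 U).

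The text before the tables bases an increase on the mean and a "dose decrease based on at least one of the three pre-breakfast plasma glucose values equal to or below 3.9 mmol/L". It does not rank the two rules.

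Table 5-4, for bolus insulin, does. Its rows for an increase and for no change both carry the condition "No SMPG below target".

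On who applies the tables, the section says: "In the weeks where no site visits are planned, subjects will adjust their insulin dose themselves". On what subjects are given: "These algorithms are provided to the subject in the diary and is part of the diabetes diary training".

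**The concern.** The mean and the minimum of three readings are different summaries, so one low value does not keep the mean low. Table 5-2 has no condition on the lowest reading and Table 5-3 has none on the mean. Some sets of readings therefore meet an increase rule and a decrease rule in the same week.

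A subject who acts on Table 5-2 in such a week raises basal insulin after a value that Section 8.4.4 requires to be recorded as a hypoglycaemic episode. The trial otherwise takes care to avoid this: it recommends a 15–20% insulin reduction at randomisation for subjects with HbA1c of 8% or less, and Section 18.1 notes more frequent and more severe hypoglycaemia when liraglutide is combined with other glucose-lowering agents. Similar glycaemic control in the two arms is also a stated aim, and that calls for one reading of the algorithm across subjects and sites.

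**Working it through.** **When both tables apply.** Table 5-3 calls for a decrease when the lowest value is ≤3.9 mmol/L. Table 5-2 calls for an increase when the mean is ≥5.1, i.e. when the three values sum to at least 3 × 5.1 = 15.3. With a low of 3.9, the other two must sum to 15.3 − 3.9 = 11.4, an average of 5.7. With a low of 3.0 they must sum to 12.3, an average of 6.15. These are ordinary readings.

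**Examples, dose ≤45 U:**

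| Readings (mmol/L) | Mean | Table 5-2 | Table 5-3 |
|---|---|---|---|
| 3.8, 5.6, 5.9 | 5.1 | +2 U | −2 U |
| 3.5, 6.5, 9.5 | 6.5 | +2 U | −2 U |
| 3.0, 7.0, 8.0 | 6.0 | +2 U | −4 U |
| 3.9, 8.0, 9.5 | 7.13 | +4 U | −2 U |
| 3.0, 12.2, 12.2 | 9.13 | +8 U | −4 U |

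At a dose of 60 U the decreases become 5% × 60 = 3 U and 10% × 60 = 6 U.

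**Search for a precedence rule.** Amendments 1 and 2 edit Section 5.3.2.2 but leave the tables and the sentence on triggers unchanged. Amendment 3 and the SAP do not address the point. Sections 5.3.2.1 and 6.5 treat lowering insulin as the response to hypoglycaemia, which shows the intended direction but is not a condition on Table 5-2.

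**How often, by assumption only.** The documents give no fasting mean, SD, distribution or day-to-day correlation, so these inputs are assumed. One million weeks of three readings were simulated per setting, with readings and their mean rounded to 0.1 mmol/L. A conflict is a lowest value ≤3.9 with a mean ≥5.1.

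| Distribution | Correlation of readings | Mean 6.0, SD 1.5 | Range over means 5.5–7.0, SDs 1.0–2.0 |
|---|---|---|---|
| Normal | 0 | 13.3% | 0.3–21.1% |
| Lognormal | 0 | 9.4% | 0.01–21.2% |
| Normal | 0.5 | 3.5% | 0.1–7.3% |
| Lognormal | 0.5 | 1.9% | 0.0–6.4% |

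At mean 6.0 and SD 1.5, the increase side is only +2 U in 98–99.9% of conflicts; over all settings the lowest share is 86.5%.

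**Weeks of self-adjustment.** Visit 2 is week 0, and visit 24 is week 56 (Section 8.1). Visits 2–24 number 23, which agrees with the 23 counselling sessions in Section 5.3.3. Visits 3–24 therefore fill 22 weeks, leaving up to 56 − 22 = 34 weeks without a site visit. Phone contacts would lower this, but the flow chart as extracted does not allow them to be counted.

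**The case against.** The strongest reply is that the text supports only one sensible reading. A single low value is a sufficient trigger for a decrease, whatever the mean. Table 5-2 has an entry for every mean of 4.0 or more, so if a low value did not override it, Table 5-3 would be uncontested only for means below 4.0. Subjects are directed to all the tables together, so raising the dose means disregarding Table 5-3. Table 5-4 can be read as showing the protocol's general principle that a low value blocks an increase. A clinician would probably infer that the decrease wins.

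There are also safeguards. Use of the algorithm is encouraged as appropriate rather than mandated, and weekly adjustment is at the investigator's discretion. At phone or face-to-face contacts the "investigator will review previous self-adjustments, and perform adjustment for the current week". Early on, "the basal dose should not exceed the pre-trial insulin dose in the first five weeks of liraglutide escalation" unless the investigator judges otherwise. Values of 3.9 mmol/L or lower must be reported, and the investigator reviews the diary for them.

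Much of this stands. Decrease-first is the better reading, the safeguards limit harm, and the simulated percentages count weeks in which the tables overlap, not weeks in which a dose is wrong. What does not follow is that the rule can stay unwritten. Review of self-adjustments comes after the dose was taken, the cap lasts five weeks, and no safeguard names the governing table for a subject adjusting alone. A table that patients apply should not depend on inference when the wrong inference raises insulin after a low reading.

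**Conclusion.** The concern holds. Two stated rules collide on the same readings, and no precedence is written in the protocol, the amendments or the SAP. That follows from the tables alone and needs no assumption.

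The size is uncertain. The percentages rest entirely on assumed glucose distributions; they show that overlap could be anything from negligible to about one week in five, and that the disputed increase is usually 2 U. Whether subjects in fact lacked guidance depends on the diary and training material, which were not available and may contain a tie-break. If they do, the protocol should say the same.

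The same tables apply to both arms, so no bias between arms is claimed. Sample size, alpha and power are not affected. The change should be made for patient safety and consistent titration.

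**What to change.** Add to Table 5-2, to the sentence on triggers in Section 5.3.2.2 and to the diary copy of the algorithm: *Increase only if none of the three SMPG values is ≤3.9 mmol/L (70 mg/dL). If any value is ≤3.9 mmol/L, use Table 5-3 only.* Apply this equally to the pre-dinner readings that set the morning dose in twice-daily users.

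Each example above then gives one instruction: −2, −2, −4, −2 and −4 U in table order. The rule also settles the milder overlap in which the mean is 4.0–5.0 (no change under Table 5-2) but one value is low, and it brings the basal rule into line with the bolus rule in Table 5-4.

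The cost is a short amendment, a diary reprint and slightly slower up-titration in weeks with a low reading.

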5.3.3 Counselling (intensive behaviour therapy)

The intensive behaviour therapy (IBT) will consist of counselling on diet, physical activity and other lifestyle modifications. The content of the IBT is based on an abbreviated version of the Diabetes Prevention Program (DPP)^{18, 19} employing the 5A counselling framework (Ask, Assess, Advise, Agree, Assist)^{20, 21}. IBT will be delivered by a registered dietician or similarly qualified healthcare professional according to local standard. The individual performing the IBT is called interventionist in this protocol. Interventionists will be trained in obesity and its behavioural management, prior to beginning the trial and will be provided on-going assistance and share better practice in how to perform IBT during the trial.

Subjects will attend a total of 23 counselling sessions during the 56 weeks period. The structure and content of each IBT session is specified in an IBT guide, consisting of an interventionist part and a subject hand out. Generally each IBT session will begin with the subject being weighed and informed of the weight change. Then the subject and interventionist will review the subject's completion of food and physical activity records (see Section 8.6.2) and the interventionist will assist with solving individual problems.

In addition to the above, each IBT session will cover a specific topic, for example, advice on diet or physical activity as well as lifestyle modification (e.g., challenging negative thoughts, obtaining social support). Most of the topics will be accompanied by a homework assignment from the IBT guide to be completed before the next session with the interventionist.

IBT sessions that cannot be completed on-site (because of illness, travel, etc.), may be completed by phone. However, this will be allowed only in exceptional cases.

Calorie targets

Caloric deficit and diet composition are aligned with clinical evidence-based guidelines for management of overweight and obesity in adults¹⁶.

Daily caloric target throughout the trial for subjects should be based on body weight at randomisation:

- Subjects weighing less than 200 lb (~90 kg) will be prescribed a diet of 1200 kcal/day
- Subjects weighing between 200 lb and 300 lb (~135 kg) will be prescribed a diet calculated as:
*Daily caloric target (kcal) = body weight (lb) * 6 (kcal/lb) or*
*Daily caloric target (kcal) = body weight (kg) * 13.23 (kcal/kg)*
- Subjects weighing more than 300 lb will be prescribed 1800 kcal/day

The initial caloric target will be kept throughout the trial. If a subject achieves a body mass index (BMI) ≤ 22 kg/m², the recommended energy intake will be re-calculated with no caloric deficit for the remainder of the trial.

The diet will consist of conventional foods with approximately 15-20% kcal from protein, 20-35% from fat, and the remainder from carbohydrate. Carbohydrate intake should be monitored by the interventionist. Carbohydrate intake from vegetables, fruits, whole grains, legumes and dairy products should be advised²².

Subjects will be instructed to record their food and calorie intake daily (see Section [8.6.2](#)).

Physical activity targets

All subjects will initially be prescribed 100 minutes physical activity per week (e.g., walking or similar aerobic activity). Subjects should be physically active in bouts of >10 minutes in duration with moderate intensity (such as brisk walking), and the physical activity should be spread equally across 4-5 days each week. Physical activity should progress gradually by 25 minutes every 4 weeks until 250 minutes/week, consistent with targets required for maintenance of lost weight²².

Subjects will be instructed to record their physical activity daily, see Section [8.6.1](#).^{18.20}

5.4 Treatment after discontinuation of trial product

When discontinuing trial products, the subject may be switched to a suitable marketed product at the discretion of the investigator.

After premature discontinuation of trial product (temporary/permanent), the subject should still remain in the trial and follow the IBT sessions and site visits if possible, see Section [8.1](#). In this case, the investigator must note down the current treatment in the medical record and eCRF. If the subject has re-started the trial product, the investigator must note down details in the medical record and eCRF, see Section [5.3.1](#).

5.5 Rationale for treatment

Subjects are treated for a period of 56 weeks in order to be able to evaluate the full effect of treatment with liraglutide 3.0 mg on the primary and secondary endpoints.

The comparator in the trial is placebo in order to evaluate the absolute safety and efficacy of liraglutide 3.0 mg.

Combining frequent behavioural counselling, highly structured hypo-caloric diets and increased physical activity is an effective tool for achieving and maintaining weight loss. It has been shown to be more effective than less intensive lifestyle modification programs for inducing weight loss²³, and

Protocol
Trial ID: NN8022-4272
UTN: U1111-1177-4903
EudraCT no.: 2015-005619-33

~~CONFIDENTIAL~~

Date: 14 September 2016
Version: 4.0
Status: Final
Page: 33 of 123

Novo Nordisk

combining IBT and pharmacologic treatment leads to more weight loss than pharmacologic treatment alone²⁴.

6 Trial population

6.1 Number of subjects

Number of subjects planned to be randomised: 400

For Mexico: The estimated number of subjects to be randomised in Mexico is 30.

6.2 Inclusion criteria

For an eligible subject, all inclusion criteria must be answered “yes”.

1. Informed consent obtained before any trial-related activities. Trial-related activities are any procedures that are carried out as part of the trial, including activities to determine suitability for the trial
2. Diagnosed with type 2 diabetes mellitus
3. Treatment with up to 2 OADs (metformin, glitazone, SGLT-2 inhibitor or sulphonylurea)
4. Stable treatment, at the discretion of the investigator, with any basal insulin according to its label (no requirement of minimum or maximum dose) for at least 90 days prior to screening
5. HbA_{1c} 6.0-10.0% (both inclusive)
6. BMI ≥ 27 kg/m²
7. Age ≥ 18 years at the time of signing informed consent
8. Maximum 5 kg self-reported weight loss within the past 90 days since screening
9. Increased physical activity is considered to be safe as judged by the investigator

6.3 Exclusion criteria

For an eligible subject, all exclusion criteria must be answered “no”.

1. Diagnosis of type 1 diabetes mellitus
2. Known hypoglycaemic unawareness as indicated by the investigator according to Clarke’s questionnaire question 8
3. Recurrent severe hypoglycaemic episodes within the last year as judged by the investigator
4. Unable or unwilling to perform self-monitoring of plasma glucose according to the protocol and to keep a diabetes diary
5. Treatment with any hypoglycaemic medications other than OADs and basal insulin within the past 90 days prior to screening
6. Treatment with a DPP-IV inhibitor within the past 90 days prior to screening
7. Recent history of cardiovascular disease (myocardial infarction or stroke within the past 6 months), severe congestive heart failure (NYHA class III, IV), or second degree or greater heart block
8. Hypersensitivity to liraglutide or any product components

9. Proliferative retinopathy or maculopathy requiring acute treatment. Verified by fundus photography or dilated fundoscopy performed within the past 90 days prior to randomisation
10. Renal impairment measured as estimated Glomerular Filtration Rate (eGFR) value of eGFR < 60 ml/min/1.73 m² as defined by KDIGO 2012 classification using isotope dilution mass spectrometry (IDMS) for serum creatinine measured at screening
11. Personal or family history of Medullary Thyroid Carcinoma (MTC) or Multiple Endocrine Neoplasia type 2 (MEN2)
12. Female who is pregnant, breast-feeding or intends to become pregnant or is of child-bearing potential and not using an adequate contraceptive method (adequate contraceptive measure as required by local regulation or practice)
For Germany: Only highly effective methods of birth control are accepted (i.e. one that results in less than 1% per year failure rate when used consistently and correctly such as implants, injectables, combined oral contraceptives, some intrauterine device), or sexual abstinence or vasectomised partner
13. Uncontrolled thyroid disease, defined as thyroid stimulating hormone (TSH) > 6 mIU/L or < 0.4 mIU/L (at screening visit)
14. Use in past 90 days since screening of medications known to induce significant weight loss (e.g., prescription weight loss medications) or weight gain (e.g., chronic use of oral steroids, second generation antipsychotics)
15. History of (or plans for) weight loss surgery (e.g. bariatric, intra-gastric balloons, maestro system) or implant of weight loss device (e.g., Reshape, vBloc). However, liposuction and/or abdominoplasty performed > 1 year before screening is allowed
16. History of pancreatitis (acute or chronic)
17. History of major depressive disorder within the past 2 years since screening
18. Diagnosis of other severe psychiatric disorder (e.g., schizophrenia, bipolar disorder)
19. A Patient Health Questionnaire-9 (PHQ-9) score of ≥ 15 at screening or randomisation
20. Any lifetime history of a suicide attempt
21. Any suicidal behaviour within the past 30 days since screening
22. Any suicidal ideation of type 4 or 5 on the Columbia-suicide severity rating scale (C-SSRS) within the past 30 days at screening or randomisation
23. Inadequately treated blood pressure defined as Grade 3 hypertension or higher (Systolic ≥ 180 mmHg or diastolic ≥ 110 mmHg)
24. History of malignancy (except for non-melanoma skin cancer) within the past 5 years
25. Any disorder, not covered by any of the other exclusion criteria, which in the investigator's opinion, might jeopardise subject's safety or compliance with the protocol
26. Known or suspected abuse of alcohol or narcotics
27. Language barrier, mental incapacity, unwillingness or inability to adequately understand or comply with study procedures, including dietary changes and physical activity
28. Subjects from the same household participating in the trial

29. Participation in any clinical trial with or without an investigational medicinal product within the past 90 days before screening
30. Previous participation in this trial. Participation is defined as signed informed consent

